5.2.3 Adverse event collection and reporting

AE Collection

The following must be collected and documented on the appropriate eCRF by the Investigator:

- From signing the informed consent onwards through the Residual Effect period (REP) which is 30 day after EOT until the end of REP all AEs (serious and non-serious) and AESIs must be reported
- After the end of REP until trial completion all related SAEs and related AESIs must be reported.

The REP is defined as 30 days after the last administration of study medication. All AEs which occurred through the treatment phase and throughout the REP will be considered as on treatment please. Events which occurred after the REP will be considered as post treatment events.

After the last per protocol contact the Investigator does not need to actively monitor patients for AEs. However, if the Investigator becomes aware of SAEs or AESIs that occurred after the last per protocol contact, the SAEs and AESIs should be reported by the Investigator to the Sponsor if considered relevant by the investigator.

Patients may be hospitalized during selected phases of the study as required per protocol, e.g., monitoring of trial drug administration, collection of blood for pharmacokinetic purposes, or for administrative reasons. Hospitalizations for administrative reasons and other hospitalizations already planned at the screening visit need not be reported as a SAE in case they are performed "as planned".

Proprietary confidential information.

© 2018 Boehringer Ingelheim International GmbH or one or more of its affiliated companies. All rights reserved.

This document may not - in full or in part - be passed on, reproduced, published or otherwise used without prior written permission.

The investigator must report the following events via telephone/fax using the SAE form immediately (within 24 hours) to the sponsor: SAEs and non-serious AEs occurring at the same time as an SAE and/or which are medically related to the SAE(s), and Protocol-specified adverse event of special interest. With receipt of any further information to these events, a follow-up SAE report has to be provided. SAEs and non-serious AEs must include a causal relationship assessment made by the investigator.

The SAE form is to be forwarded to the defined unique entry point identified for the BI OPU (country-specific contact details will be provided in the Investigator Site File) or by using the electronic submission process. This immediate report is required irrespective of whether the investigational product has been administered or not and irrespective of causal relationship. It also applies if new information to existing SAEs or AESIs becomes available.

AE reporting to sponsor and timelines

The investigator must report SAEs, AESIs, and non-serious AEs which are relevant for the reported SAE or AESI, on the BI SAE form via fax immediately (within 24 hours) to the Sponsor's unique entry point (country specific contact details will be provided in the ISF). In specific occasions the Investigator could inform the Sponsor upfront via telephone. This does not replace the requirement to complete and fax the BI SAE form.

Information Required

For each AE, the investigator will provide information requested on the appropriate eCRF pages and the BI SAE form, e.g. onset, end date, intensity, treatment required, outcome, seriousness, and action taken with the investigational drug(s). The investigator should determine the causal relationship to the trial medication, the trial procedures outlined under [Section 6.2](#).

The following should also be records as an SAE in the eCRF and SAE form (if applicable):

- Worsening of pre-existing conditions unless due to underlying disease
- Changes in vital signs, ECG, physical examination and laboratory test results, if they are judged clinically relevant by the Investigator.

If such abnormalities already pre-exist prior trial inclusion they will be considered as baseline conditions.

Screening Failures

SAEs occurring in patients having discontinued the trial due to screening failures, i.e. after the screening period and who did not receive any trial medication, are to be reported if the Investigator considered the SAE related to the screening procedure. SAEs which occurred during the screening period are to be reported according to standard procedures.

Pregnancy

Proprietary confidential information.

© 2018 Boehringer Ingelheim International GmbH or one or more of its affiliated companies. All rights reserved.

This document may not - in full or in part - be passed on, reproduced, published or otherwise used without prior written permission.

In the rare case that a female subject participating in this clinical trial becomes pregnant after having taken trial medication, the Investigator must report immediately (within 24 hours) the drug exposure during pregnancy (DEDP) to the Sponsor's unique entry point (country-specific contact details will be provided in the ISF). The Pregnancy Monitoring Form for Clinical Trials (Part A) should be used.

The outcome of the pregnancy associated with the drug exposure during pregnancy must be followed up and reported to the Sponsor's unique entry point on the Pregnancy Monitoring Form for Clinical Trials (Part B).

As pregnancy itself is not to be reported as an AE, in the absence of an accompanying SAE, only the Pregnancy Monitoring Form for Clinical Trials and not the SAE form is to be completed. If there is an SAE associated with the pregnancy then the SAE has to be reported on the SAE form in addition.

The ISF will contain the Pregnancy Monitoring Form for Clinical Trials (Part A and B).

Exemption to SAE Reporting

Disease Progression in oncology trials is a study endpoint for analysis of efficacy. Disease progression (malignant neoplasm progression, neoplasm progression) is exempted from reporting as a (S)AE. Progression of the subject's underlying malignancy will be recorded in the appropriate pages of the (e)CRF as part of efficacy data collection. Death due to disease progression is to be recorded on the appropriate CRF page and not on a SAE form.

Examples of exempted events of PD are:

- Progression of underlying malignancy (Progressive disease PD): if PD is clearly consistent with the suspected progression of the underlying malignancy as defined by the respective response criteria.
- Hospitalization/Procedures due solely to the progression of underlying malignancy (PD)

Clinical symptoms and/or signs of progression (with or without confirmation by objective criteria e.g. imaging, clinical measurement): if the symptom can exclusively be determined to be due to the progression of the underlying malignancy and does meet the expected pattern of progression for the disease under study.

Please note, when there is evidence suggesting a causal relationship between the drug and the progression of the underlying disease, the event must be reported as (S)AE.

Exempted events are monitored at appropriate intervals by an independent committee such as the Safety Monitoring Committee. All SAEs, including those persisting after trial completion must be followed up until they have resolved, have been sufficiently characterized, or no further information can be obtained.

Proprietary confidential information.

© 2018 Boehringer Ingelheim International GmbH or one or more of its affiliated companies. All rights reserved.

This document may not - in full or in part - be passed on, reproduced, published or otherwise used without prior written permission.

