5.2.2 Assessment of adverse events

5.2.2.1 Definitions of adverse events

Adverse event

An adverse event (AE) is defined as any untoward medical occurrence in a patient or clinical investigation subject administered a pharmaceutical product and which does not necessarily have a causal relationship with this treatment.

An AE can therefore be any unfavourable and unintended sign (including an abnormal laboratory finding) symptom, or disease temporally associated with the use of a medicinal product, whether or not considered related to the medicinal product.

Serious adverse event

A serious adverse event (SAE) is defined as any AE which:

- results in death,
- is life-threatening,
- requires inpatient hospitalization or prolongation of existing hospitalization,

Proprietary confidential information.

© 2018 Boehringer Ingelheim International GmbH or one or more of its affiliated companies. All rights reserved.

This document may not - in full or in part - be passed on, reproduced, published or otherwise used without prior written permission.

- results in persistent or significant disability or incapacity,
- is a congenital anomaly/birth defect,

or

- is to be deemed serious of any other reason it is an important medical event when based upon appropriate medical judgement which may jeopardize the patient and may require medical or surgical intervention to prevent one of the other outcomes listed in the above definitions.

Life-threatening in this context refer to an event in which the patient was at risk of death at the time of the event; it does not refer to an event that hypothetically might have caused death if more severe.

AEs considered “Always Serious”

In accordance with the European Medicines Agency initiative on Important Medical Events, Boehringer Ingelheim has setup a list of AEs, which by their nature, can always be considered to be “serious” even though they may not have met the criteria of an SAE as given above.

The latest list of “Always Serious AEs” can be found in the RDC system. These events should always be reported as SAEs as described in [Section 5.2.3](#).

Adverse Events of special interest (AESIs)

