5.2.5 Electrocardiogram

A 12-lead resting electrocardiogram (ECG) will be performed in **all patients** at the screening visit and at the beginning of each cycle (except for cycle 1) and at the EOT visit. The ECG will be assessed for pathological results (to be recorded as either baseline condition, concomitant disease or AE) by the investigator. Additional examinations should be done whenever the investigator deems necessary.

For safety monitoring 12-lead ECGs (I, II, III, aVR, aVL, aVF, V1 - V6) will be recorded using an electrocardiograph.

All ECGs will be recorded for a 10 second duration after the subjects have rested for at least 5 min in a supine position.

Proprietary confidential information.

© 2018 Boehringer Ingelheim International GmbH or one or more of its affiliated companies. All rights reserved.

This document may not - in full or in part - be passed on, reproduced, published or otherwise used without prior written permission.

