7.8.1 Adverse events

Unless otherwise specified, the analyses of adverse events will be descriptive in nature. All analyses of AEs will be based on the number of subjects with AEs and NOT on the number of AEs.

For analysis multiple AE occurrence data on the CRF will be collapsed into an AE provided that all of the following applies:

- All AE attributes are identical (LLT, intensity, action taken, therapy required, seriousness, reason for seriousness, relationship, outcome, AE of special interest)
- The occurrences were time-overlapping or time-adjacent (time-adjacency of 2 occurrences is given if the second occurrence started on the same day or on the day after the end of the first occurrence).

For further details on summarization of AE data, please refer to [\[3, 4\]](#).

The analysis of adverse events will be based on the concept of treatment emergent adverse events. That means that all adverse events occurring between first drug intake till last drug intake + residual effect period will be assigned to the treatment. All adverse events occurring before first drug intake will be assigned to 'screening' and all adverse events occurring after the residual effect period will be assigned to 'post-treatment' (for listings only). For details on the treatment definition, see [Section 6.1](#).

According to ICH E3 [\[5\]](#), AEs classified as 'other significant' needs to be reported and will include those non-serious adverse events leading to treatment discontinuation or non-serious AEs leading to dose reduction.

An overall summary of adverse events will be presented. This summary will include the first 6 categories from the list below and AEs by highest intensity graded according to CTCAE (version 4.03).

The frequency of subjects with adverse events will be summarised by treatment, primary system organ class and preferred term (mention MedDRA levels to be displayed in the tables).

Separate tables will be provided for patients with each of the following AE categories:

- All AEs,
- DLTs (Course 1 only¹),
- DLTs (All courses),
- AEs leading to dose reduction,

- AEs leading to treatment discontinuation,
- Serious AEs,
- Drug related AEs,
- Drug related serious AEs,
- CTCAE Grade 3 or higher AEs,
- AEs leading to death,

[1]: Course 1 defined by from start of treatment to start of Cycle 2 or the last dose administration of BI 836909 during Cycle 1 + 30 days, whichever occurs earlier.

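### Protocol Section 5.2.3 tells sites to record clinically relevant findings as SAEs with no seriousness condition, contradicting the SAE definition in Section 5.2.2.1

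*Protocol*

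**What the plan says.** Under 'Information Required', Protocol Section 5.2.3 first lists what the investigator provides for each AE, including seriousness. It then says "The following should also be records as an SAE in the eCRF and SAE form (if applicable", followed by two items: "Worsening of pre-existing conditions unless due to underlying disease" and "Changes in vital signs, ECG, physical examination and laboratory test results, if they are judged clinically relevant by the Investigator". The only other limit is that abnormalities present before inclusion count as baseline conditions.

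Section 5.2.2.1 begins its definition with "A serious adverse event (SAE) is defined as any AE which" and lists death, threat to life, hospitalisation or its prolongation, disability, congenital anomaly and the important medical event. It adds a sponsor list of events that are always serious.

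Elsewhere such findings are AEs:
- The AE definition in Section 5.2.2.1 covers "any unfavourable and unintended sign (including an abnormal laboratory finding".
- Section 5.2.5 says a pathological ECG is "to be recorded as either baseline condition, concomitant disease or AE".
- SAP 7.8.4 says an adverse event was recorded where an ECG readout had a clinical finding.

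SAP 7.8.1 plans separate tables for serious AEs and for "Drug related serious AEs". It also plans one for 'other significant' AEs, defined as non-serious AEs leading to treatment discontinuation or dose reduction.

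**The concern.** Two operative sections give a site different answers for the same event. Take a laboratory change that the investigator thinks clinically relevant but that meets no seriousness criterion and is not on the Always Serious list. Section 5.2.2.1 makes it a non-serious AE. Section 5.2.3 has it recorded as an SAE. A site cannot comply with both.

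What is at stake is the meaning of the SAE outputs. The serious and drug-related serious AE tables should describe seriousness. If part of their content depends on which sentence a site followed, differences between dose cohorts may reflect coding habits. Each such record also enters 24-hour reporting and SAE follow-up under Section 5.2.3. The safety committee reviews all available safety data before each escalation (Section 3.1.1), so the coding would be visible there too.

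**Working it through.** The plan states no SAE rate, so there is no figure to reproduce. The check is a comparison of texts, then the direction of the effect, then the size of one recoded patient.

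**1. Is clinical relevance a seriousness criterion?** No. The nearest criterion is the one based on judgement, "is to be deemed serious of any other reason it is an important medical event when based upon appropriate medical judgement". It goes on to require that the event may jeopardise the patient and may need intervention to prevent one of the other listed outcomes. That is narrower than a finding the investigator considers clinically relevant. Some listed findings will meet it, but not all need to.

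**2. Does the bracket supply the missing condition?** '(If applicable)' follows 'SAE form' and most naturally qualifies the form. That leaves the instruction to record an SAE in the eCRF standing. If it is read as 'if serious', the sentence says only that SAEs are SAEs. Neither reading tells the site when to code a finding as serious.

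**3. Does another passage correct it?** None does. The limits in Section 5.2.3 concern underlying disease, abnormalities existing before inclusion and, later in the section, disease progression. Section 5.2.5 and SAP 7.8.4 use the AE route for ECG findings but do not mention the sentence.

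**4. Direction.** Let p be the share of a cohort with an SAE under Section 5.2.2.1, and q the share of the remaining patients with a listed but non-serious finding.

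- SAE incidence under Section 5.2.2.1: p
- SAE incidence under Section 5.2.3 taken literally: p + (1 − p)q
- Difference: (1 − p)q, which is never negative

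The sentence adds events and removes none, so the direction is certain if it is followed. The documents give neither p nor q, so the difference has no derivable value.

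**5. Effect of one recoded patient.** Protocol Table 3.1:1 gives 3 (+3) patients per cohort from 3.2 µg/day upwards, and Section 3.1 allows up to 6 more at the MTD or recommended dose.

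- 3 patients: 1/3 = 33 percentage points
- 6 patients: 1/6 = 17 percentage points
- 6 + 6 = 12 patients: 1/12 = 8 percentage points

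**6. Which tables move.** An event wrongly coded serious enters the serious AE table and, if judged related, the drug-related serious AE table. If it led to discontinuation or dose reduction, it also leaves the 'other significant' table, which takes only non-serious events.

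**7. The primary endpoint.** Section 5.2.1.1 defines DLT mainly by drug-relatedness and CTCAE grade, with listed exceptions and additions. Section 5.2.1 derives the MTD from DLTs in cycle 1. Seriousness enters neither.

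**The case against.** The strongest reply is that 'SAE' is a slip for 'AE'. The sentence follows directly on a paragraph about each AE, contains another typing error, and has a bracket that fits better if its first term is AE. The visit tables in Section 6.2.4 likewise record new myeloma symptoms as an AE when applicable. A sensible site might read it so. Seriousness is also collected separately for each AE, SAP 7.8.1 lists both seriousness and its reason as AE attributes, and monitors check eCRF data against source (Section 3.1.1).

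Much of this stands. A slip is likely, and it is a reason to correct the sentence, because the operative text still says SAE. The other safeguards do not settle the matter. Monitoring compares the eCRF with source, and a site that codes as Section 5.2.3 instructs has not deviated from the protocol. A separate seriousness field helps find such records afterwards but does not tell the site how to fill it in.

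A reader might infer three stronger things that the documents do not support:
- **That SAE incidence is inflated, perhaps to nearly every patient at active doses.** This depends on sites following the sentence, and no rate is given. Section 2.3 says only that white cell changes and cytokine release may occur, and only changes judged clinically relevant count.
- **That ordinary fever becomes a spurious SAE.** Section 4.2.1.2.3 has patients hospitalised for fever above 38.3°C, or above 38°C sustained for at least an hour. Hospitalisation is itself a seriousness criterion, so much clinically relevant fever could be an SAE anyway.
- **That the MTD or recommended dose is distorted.** DLT and MTD do not use seriousness, and the safety committee reviews all available data, not SAE percentages alone.

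**Conclusion.** The point holds as an internal contradiction in current protocol text. Section 5.2.3 directs non-serious findings to SAE status; Section 5.2.2.1 does not, and Section 5.2.5 and SAP 7.8.4 use the AE route for ECG findings.

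Two consequences are conditional. If sites follow the sentence literally, the serious and drug-related serious AE tables can only gain non-serious events, and the 'other significant' table can only lose them. If the sites (five are planned, Section 3.3) read it differently, SAE coding varies by site. How many patients would be affected cannot be derived from the documents; the 8 to 33 percentage points describe one recoded patient who has no other SAE.

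This rests on reading '(if applicable)' as attached to the form, and on some clinically relevant findings meeting neither a seriousness criterion nor the Always Serious list. The analyses are descriptive and the primary endpoint is not directly affected. The correction is still worth making, because it changes what is recorded and tabulated.

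**What to change.** Replace the introductory sentence in Section 5.2.3 with wording such as: *The following should also be recorded as an AE in the eCRF, and as an SAE (with SAE form) if a seriousness criterion or the Always Serious list in 5.2.2.1 applies. SAE-form reporting of AESIs, and of non-serious AEs relevant to an SAE or AESI, is unchanged.*

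The last part is needed. Sections 5.2.2.1 and 5.2.3 put AESIs on the SAE form whether or not they are serious, and hepatic injury is an AESI defined by laboratory values. Restricting the form to serious events would create a new conflict and could drop such cases from 24-hour reporting.

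Before database lock, list the SAEs whose only apparent basis is the Section 5.2.3 list, using the reason-for-seriousness attribute named in SAP 7.8.1. Ask the investigator to confirm which criterion applies. The investigator supplies seriousness, so the sponsor should not downgrade an event on its own.

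The cost is one sentence, one listing and the time to answer the queries. No analysis method or table shell changes.

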5.2.4 Assessment of safety laboratory parameters

5.2.4.1 General safety laboratory parameters

Blood samples and urine have to be collected at the time points specified in the [flowchart](#). Safety laboratory examinations will include haematology, biochemistry, coagulation and qualitative urine analysis. **The measurements will be performed locally.**

| | |
|--------------|---|
| Haematology | Haemoglobin, red blood cell count (RBC), white blood cell count (WBC) with differential, platelets (PLT) |
| Biochemistry | Glucose, sodium, potassium, total calcium, inorganic phosphate, creatinine, aspartate amino transferase (AST), alanine amino transferase (ALT), alkaline phosphatase (AP), lactate dehydrogenase (LDH), total bilirubin (if elevated provide direct bilirubin), urea, total protein, albumin, uric acid, Ferritin (at baseline of cycle 1 only). Serum immunoglobulin levels (IgG, IgM, IgA) at baseline, day 15 and day 29 of each cycle only |
| Coagulation | Activated partial thromboplastin time (aPTT), prothrombin time (PT)/international normalised ratio (INR), fibrinogen and D-Dimers in cycle 1 and 2; thereafter on day 1 of each of the following cycles only. |
| Urine | pH, glucose, erythrocytes, leukocytes, protein, nitrite will be analysed by dipstick and reported as semiquantitative measurements. In case of pathological findings, further evaluation should be performed and results documented. |

A serum pregnancy test needs to be obtained at the time points indicated in the [flowchart](#) in patients of childbearing potential.

In case a treatment course is delayed due to an adverse event, the patient should visit the site at least once a week for assessment of safety laboratory and adverse events. More frequent visits may be appropriate as assessed by the investigator.

